3.2 Drug Accountability and Compliance

For each randomized patient 8 drug preparations (posaconazole or placebo) will be delivered by the hospital pharmacy. The amount of used and non-used posaconazole vials will be stated in a drug accountability log.

3.3 Concomitant medication / Prohibited Medication

Medication for the treatment of common adverse events related to posaconazole treatment such as headache, abdominal pain, nausea, diarrhea, constipation, vomiting, cough and dyspnoea are permitted concurrently with the trial medication. Other treatments related to standard of care of critically ill influenza patients are allowed during treatment with posaconazole, taking in to account the precautions below.

Patients being treated with the following medication should be continuously monitored for AEs: sirolimus, CYP3A4 substrates (pimozide, quinidine), HMG-CoA Reductase Inhibitors Primarily Metabolized Through CYP3A4 (simvastatin), ergot alkaloids (ergotamine and dihydroergotamine), vincristine, terfenadine, cisapride, ebastine, astemizole, cimetidine, rifampin, carbamazepine, phenytoin, rifabutin, barbiturates, isoniazid and anthracyclines.

[figure not shown]
In patients being treated with calcineurin-inhibitors (cyclosporine or tacrolimus) frequent monitoring of cyclosporine and tacrolimus whole blood concentrations should be performed during and at discontinuation of posaconazole treatment since elevated concentrations of these drugs can lead to nephrotoxicity and leukoencephalopathy. Cyclosporine and tacrolimus dosing should be adjusted according to their whole blood concentrations.

4 Eligibility Criteria

4.1 Inclusion criteria

Patients eligible for inclusion in this trial have to meet **all** of the following criteria:

1. Written informed consent must be obtained from the patient or his/her legal representative prior to any study procedures
2. Adult patient (≥ 18 years)
3. PCR-confirmed influenza based on nasopharyngeal swab (NS), bronchial aspirate (BA) or broncho-alveolar lavage (BAL) within 7 days before ICU admission or within 48 hours after ICU admission.
If PCR is not available a positive result of a rapid test is required (a negative rapid test does not imply absence of influenza and thus requires confirmation by PCR)
4. Influenza symptoms present for no more than 10 days before ICU admission
5. Respiratory distress as the main reason for ICU admission. Respiratory distress will be defined as tachypnea with an respiratory rate ≥ 25 x/min and a $\text{paO}_2/\text{FiO}_2$ -ratio ≤ 300 with or without (bilateral) infiltrates.

4.2 Exclusion criteria

Patients eligible for this trial must not meet any of the following criteria:

1. Patients with age < 18 years
2. Pregnant women (based on a positive serum sample)
3. Expected survival on ICU admission ≤ 48 h
4. Patients having influenza symptoms for more than 10 days before ICU admission
5. Patients being transferred from another hospital ward or another hospital who already have mycological evidence for an IAA-infection (based on sputum, BA or BAL culture, BAL or serum GM)
6. Patients with known intolerance or hypersensitivity to posaconazole or other azole antifungal agents
7. Patients that are being treated actively with antifungal agents for invasive aspergillosis
8. Patients with a QTc interval ≥ 500 msec
9. Patients with liver cirrhosis (Child C)
10. Participation in another interventional clinical trial

11. Any disorder, which in the investigator's opinion might jeopardise subject's safety or compliance with the protocol
12. Patients or their legal representatives who did not sign the informed consent form

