As influenza virus infection leads to lysis of infected cells, we believe that a severe influenza infection causes cytopathology of the epithelial lining of the trachea and bronchi, providing *A. fumigatus* the opportunity for invasive growth. Many patients developed invasive *Aspergillus* tracheobronchitis, which is a manifestation of invasive aspergillosis that is difficult to diagnose due to lack of specific radiologic features.[3] Furthermore, influenza may contribute to a hyperinflammatory status known as macrophage activation syndrome that contributes to pulmonary damage.[4] Disruption of anatomical barriers and the dysregulated host defense provides an opportunity for *A. fumigatus* to cause fulminant invasive disease. Although biomarkers, such as galactomannan, in BAL and serum are useful tools in diagnosing IAA, early diagnosis proved difficult in the above-mentioned Dutch observational study. Moreover, the median time to initiation of antifungal therapy after influenza diagnosis in survivors and non-survivors was two days versus nine days ($P<0.06$), which underscores that early intervention is critical for survival. Finally, a high azole resistance rate of 29% was observed in these Dutch ICUs, which further complicates patient management.[2,5]

Therefore we propose to perform **an interventional non-blinded randomized controlled multicentric Dutch-Belgian proof-of-concept interventional study** in patients with severe influenza admitted to the ICU, randomizing patients either to oseltamivir therapy with standard care for diagnosis and treatment of secondary infectious complications or to oseltamivir plus posaconazole prophylaxis.

Currently there is no mold-active antifungal agent licensed for prophylaxis of invasive mold disease in ICU patients. The antifungal azole posaconazole is the drug of choice for antifungal prophylaxis in neutropenic patients with acute myeloid leukemia and those with graft-versus host disease following allogeneic HSCT.[6,7] These studies showed that posaconazole prophylaxis reduced the prevalence of invasive aspergillosis to below 2% in these high risk patients. Posaconazole is however not licensed for prophylaxis in other patient groups, i.e. critically ill patients. Based on the experience in patients with hematological

malignancy we anticipate that posaconazole prophylaxis will be effective to reduce the IAA incidence and eventually outcome in patients at risk for IAA.

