7.1 Sample Size

Based on an estimated IAA incidence of 25% and considering a 80% reduction of the incidence (to 5%) caused by posaconazole prophylaxis and a power of 80%, a sample size calculation showed that 47 patients in each study arm are needed. Because it is impossible that the use of posaconazole will increase the

incidence of IA, a one-sided p-value was used for this sample size calculation. To include at least 100 patients in the MITT endpoint analysis, 110 patients will be included in the study (55 in each arm).

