7.2 Data Analysis

Appropriate statistical tools will be used to test for significance with respect to the primary and secondary endpoints.

Categorical variables will be reported as a percentage and continuous variables as mean \pm standard deviation (SD) or median and interquartile range (IQR), as appropriate. Differences in categorical variables will be assessed using the Chi squared test or the Fischer's Exact test and for the analysis of continuous variables the Student's t test or the Mann-Whitney U test will be used, where appropriate. P values <0.05 are considered significant. Patients that die during the trial duration will also be included in the statistical analysis.

The primary endpoint analysis will consist of a one-sided fisher-exact test in which the proportion of cases of IAA will be compared between both groups. The population included in this analysis will consist of a modified intent to treat population. This MITT population consists of all patients that received at least 1 posaco/placebo administration but excluding the patients in which a diagnosis of IAA was made on the basis of the BAL sample taken on day 1 because these patients in fact had an IAA at the day of inclusion.

8 Data handling

Patient data will be encoded: which means that personal data can only be related to an identified or identifiable person by means of a code.

Demographic, biochemical, microbiological and radiological data will be collected prospectively as a part of clinical routine. Samples will be obtained for characterization of the influenza type and for *Aspergillus* diagnosis including culture, galactomannan and PCR. These samples are part of daily routine, no additional samples for this study will be taken. All *Aspergillus* colonies will be screened for azole resistance, using an agar-based selection tool, and relevant samples, i.e. BAL fluid, will be stored for direct detection of resistance mutations by PCR. Clinical *A. fumigatus* isolates will be sent the National Mycology Reference Laboratory in Leuven (Belgium) or Nijmegen (the Netherlands) for MIC-testing and analysis of azole-resistance mutations. A blinded data review committee following a pre-defined case definition will classify patients with evidence for primary and breakthrough IAA-infection.

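### Exclusion 7 covers only antifungal treatment of aspergillosis, so patients already on mould-active prophylaxis can be randomised and dilute the contrast in proportion to their unknown share

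*Combined protocol and SAP*

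**What the plan says.** Exclusion 7 in section 4.2 reads "Patients that are being treated actively with antifungal agents for invasive aspergillosis". No other criterion reaches current antifungal use. Exclusion 5 concerns transferred patients who already have mycological evidence, exclusion 6 concerns intolerance to azoles, and exclusion 11 concerns a disorder that might jeopardise safety or compliance. Haematological malignancy and transplantation are not excluded.

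The background section states that "The antifungal azole posaconazole is the drug of choice for antifungal prophylaxis in neutropenic patients with acute myeloid leukemia" and names graft-versus-host disease after allogeneic transplantation as a second such group. The protocol therefore itself identifies patients who could arrive in ICU already on prophylaxis.

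Section 3.3 says "Other treatments related to standard of care of critically ill influenza patients are allowed during treatment with posaconazole", subject to precautions. Its visible text names no antifungal as prohibited and sets no rule for the SOC arm. It does give monitoring instructions for patients on cyclosporine, tacrolimus, sirolimus, vincristine and anthracyclines, so transplant and chemotherapy patients are expected in the trial.

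Section 2.1 gives the objective as antifungal prophylaxis added to SOC, compared with SOC alone. The SOC description in section 2.4 does not mention antifungal prophylaxis.

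**The concern.** A patient on mould-active prophylaxis at randomisation cannot show the contrast that section 2.1 sets out. If allocated to SOC, the patient is on prophylaxis anyway. If allocated to posaconazole, the patient does not move from no prophylaxis to prophylaxis.

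Nothing later in the plan deals with this. Section 5.4 describes block randomisation and names no stratification factor. The modified intention-to-treat rule in section 7.2 removes only patients whose IAA was diagnosed on the day-1 BAL. No analysis uses antifungal exposure at baseline.

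What is at stake is power. The trial is small and its sample size rests on a large assumed effect, so a modest rise in the number of uninformative patients can use up the margin.

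**Working it through.** **Inputs from the documents.** Section 7.1: "Based on an estimated IAA incidence of 25" per cent, "considering a 80% reduction of the incidence (to 5%) caused by posaconazole prophylaxis", 80% power, and "a one-sided p-value was used for this sample size calculation". It concludes that "47 patients in each study arm are needed" and plans 110 patients so that at least 100 (50 per arm) enter the primary analysis. Section 7.2: a one-sided Fisher exact test, and "P values <0.05 are considered significant". Section 7.1 states no alpha, so I take one-sided 0.05.

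**Reproducing the plan's figure.** Pooled-variance formula for two proportions, mean rate (0.25 + 0.05)/2 = 0.15:

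n' = [1.645·√(2·0.15·0.85) + 0.842·√(0.25·0.75 + 0.05·0.95)]² / 0.20² = 38.35

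With continuity correction:

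n = (n'/4)·[1 + √(1 + 4/(n'·0.20))]² = 47.8, or 48 per arm

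This agrees with the stated 47 to within one patient. Exact one-sided Fisher power, by full enumeration of both binomial distributions, is 82.7% at 47 per arm and 85.3% at 50 per arm.

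**Dilution model.** Let f be the share of patients already on mould-active prophylaxis. The documents give no value, so f is a purely assumed range. Three further assumptions are needed:
- 25% is the rate in unexposed patients.
- Ongoing prophylaxis is as effective as trial drug (5% rate).
- Exposed patients would have the same 25% risk if untreated.

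Then

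SOC rate = 0.25(1 − f) + 0.05f = 0.25 − 0.20f

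and the posaconazole arm stays at 5%.

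| Assumed f | SOC rate | Difference (points) | Exact power, 50 per arm |
|---|---|---|---|
| 0% | 25% | 20 | 85.3% |
| 5% | 24% | 19 | 82.3% |
| 10% | 23% | 18 | 78.9% |
| 15% | 22% | 17 | 75.1% |
| 20% | 21% | 16 | 70.9% |

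At f = 7.5% (SOC rate 23.5%) power is 80.7%, so the plan keeps its stated 80% up to a share of roughly 8%.

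**Two ways of removing the dilution.**
- *Exclusion at screening.* The places go to unexposed patients, so 50 per arm at 25% versus 5% is kept: 85.3%.
- *Omission at analysis only.* Patients per arm fall to 50(1 − f). At f = 10% that is 45 per arm and 80.7%, against 78.9% with the exposed patients left in. At f = 20% it is 40 per arm and 75.0%, against 70.9%.

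**The case against.** **The share may be small.** The documents do not support any particular f. The background section says that no mould-active agent is licensed for prophylaxis in ICU patients, and that 7 of the 23 IAA patients in the Dutch cohort had been previously healthy. This stands: shares of 10% to 20% are assumptions. The licensing remark does not close the gap, because these patients would arrive on prophylaxis begun for another reason.

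**The 25% may already include such patients.** Section 7.1 does not say to whom the rate applies. The Dutch cohort (23 of 144, 16%) is described without any exclusion for earlier antifungal use. If 25% is an all-comer rate, the model counts part of the dilution twice. This stands as a limit on the size.

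**Background prophylaxis could be part of SOC.** On the add-on wording of section 2.1, keeping these patients is a pragmatic design choice. That is arguable, but section 2.4 does not describe SOC in those terms, and the choice is not stated anywhere.

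**Exposure is partly recorded.** The trial flowchart has a concomitant-medication row, and section 8.1 lists concomitant medication among the data to be confirmed in the CRF. This stands: collection is not what is missing. Its use in eligibility or analysis is.

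**Stronger readings.** A reader might infer that the gap erases the trial's contrast. That holds only for the individual exposed patient; for the trial it would require every SOC patient to be on prophylaxis. A reader might also infer a biased or false-positive result. Exposure precedes randomisation and is expected to balance between arms, so the expected effect is attenuation towards the null. Nor do the documents show that the trial is underpowered, since that depends on an unreported share. Finally, section 3.3 contains a figure that is not shown, so the absence of an antifungal restriction there can be claimed only for its visible text.

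**Conclusion.** The gap in eligibility is real, and no visible text elsewhere closes it. Patients on mould-active prophylaxis can be randomised, and they dilute the comparison in proportion to their share.

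Under the stated assumptions the loss is minor at a 5% share (3.0 points of power, 85.3% to 82.3%). Power falls just below the planned 80% at a 10% share, and clearly below it at 20% (70.9%). These figures depend on an assumed share, on equal efficacy and equal untreated risk, and on 25% being the rate in unexposed patients. If 25% describes all comers, the true loss is smaller. The point does not threaten the validity of the trial, but the change is worth making because the main remedy is a single line.

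**What to change.** **Main change.** Extend exclusion 7 to any systemic mould-active antifungal in use at screening, whether for treatment or prophylaxis. This concerns eligibility only and implies nothing about how those patients should be treated. Recruitment continues to the same target, so 50 per arm in the primary analysis and 85.3% power under the plan's own assumptions are kept. The cost is one eligibility line and a loss of eligible patients that is probably small but unknown. If the share turns out to be large, that loss grows with it, and so does the dilution avoided.

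**Fallback if the sponsor prefers to keep these patients.** State that choice. Use the concomitant-medication data already collected to flag mould-active exposure at randomisation in both arms, and pre-specify an analysis without the flagged patients. Because the flag is a baseline variable, the restriction does not introduce post-randomisation selection. The gain in power is small, under 2 points at a 10% share and about 4 points at 20%, because the sample shrinks. At 20% it does not restore the planned 80%. The cost is one derived variable and one pre-specified analysis.

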4.3 Criteria for premature discontinuation of trial product

- Safety concerns related to trial product (see paragraph 6) or unacceptable intolerance.
- Included in the trial in violation of the inclusion and/or exclusion criteria
- Pregnancy
- Simultaneous participation in another clinical trial of an approved or non-approved investigational medicinal product (IMP)

4.4 Withdrawal criteria

The subject may withdraw consent at will at any time. The subject's request to withdraw from the trial must always be respected. Patients will also be withdrawn from the study when an IAA-infection is diagnosed based on clinical and mycological evidence with radiological abnormalities, between day 1 and day 7 of posaconazole prophylaxis. At that time antifungal treatment will be started. The type and duration of antifungal therapy will be at the discretion of the treating physician.

5 Trial Procedures

5.1 Selection of Participants / Recruitment

Patients admitted to ICU with a severe influenza pneumonia will be screened by the study nurse. When all eligibility criteria are met, the PI or the treating physician will approach the patient or his/her relatives in order to give study information and request informed consent.

5.2 Consent

The Principal Investigator (PI) retains overall responsibility for the informed consent of participants at their site and must ensure that any person delegated responsibility to participate in the informed consent process is duly authorised, trained and competent to participate according to the ethically approved protocol, principles of Good Clinical Practice (GCP) and Declaration of Helsinki. If delegation of consent is acceptable then details should be provided. Adequate documentation will be performed.

Informed consent must be obtained prior to the participant undergoing procedures that are specifically for the purposes of the trial and are out-with standard routine care at the participating site (including the collection of identifiable participant). All obtained original informed consent forms must remain at the site and cannot be destroyed (even when a scanned copy is available).

The right of a participant to refuse participation without giving reasons must be respected. The participant must remain free to withdraw at any time from the trial without giving reasons and without prejudicing his/her further treatment and must be provided with a contact point where he/she may obtain further information about the trial. Where a participant is required to re-consent or new information is required to be provided to a participant it is the responsibility of the PI to ensure this is done in a timely manner.

The PI takes responsibility for ensuring that all vulnerable subjects are protected and participate voluntarily in an environment free from coercion or undue influence. Where the participant population is likely to include a significant proportion of participants who cannot read or write, require translators or have cognitive impairment, appropriate alternative methods for supporting the informed consent process should be employed. This may include allowing a witness to sign on a participant's behalf (in the case of problems with reading or writing), designate a legal representative, or providing Participant Information Sheets in other languages or in a format easily understood by the participant population (in the case of minors or cognitive impairment) providing they are approved by the EC.

5.3 Expected Duration of the Trial

The expected duration of the trial will be 90 days. If the patient is not hospitalized any more at the 90th day after randomization, the patient or his/her relatives will be contacted by telephone in order to obtain 90-day mortality data.

5.4 Randomisation Procedure / Code Break / Allocation concealment

Patients will be randomly assigned to the posaconazole prophylaxis group or the SOC group by using the Sealed Envelope randomization procedure (www.sealedenvelope.com). Block randomization will be used.

5.5 Visit schedule and assessments

5.5.1 Screening/ Baseline

After eligibility screening and signing the trial ICF, the following screening assessments will be done:

- Patient demographics and baseline parameters (SOC)
- Medical History (SOC)

5.5.2 Treatment Visits

Day 1 = day of randomization:

- Bronchoscopy with BAL sampling, serum galactomannan (SOC)
- Pregnancy screening negative
- Start study medication
- Gather baseline clinical data including demographic, biochemical, microbiological and radiological data (SOC)

Day 2 – ICU discharge:

- Withdrawal of patients from study if mycological evidence of IAA-infection on BAL of day 1
- Continuation of study medication up to day 7
- Gather clinical data including demographic, biochemical, microbiological and radiological data (SOC)
- Assess presence of IAA-infection (SOC)
- Assess outcome parameters: ICU mortality, IAA-infection (SOC)

30 days after randomization:

Assess outcome parameters: hospital and/or 30-day mortality and a retrospective assessment of IAA-infection (SOC)

90 days after randomization:

- Assess outcome parameters: hospital and/or 90-day mortality and a retrospective assessment of IAA-infection (SOC)

5.5.3 Discontinuation of Treatment – End of Trial Visit – Withdrawal of Consent

Patients may voluntarily discontinue from the trial treatment for any reason at any time. If a patient decides to discontinue from the trial treatment, the investigator must make a reasonable effort (e.g. telephone, e-mail, letter) to understand the primary reason for this decision and record this information in the patient's chart and on the appropriate CRF pages. They may be considered withdrawn if they state an intention to withdraw, fail to return for visits, or become lost to follow-up for any other reason. The investigator should discontinue trial treatment for a given patient if, he/she believes that continuation would be detrimental to the patient's well-being.

Patients may voluntarily withdraw consent to participate in the trial for any reason at any time. Withdrawal of consent occurs only when a patient does not want to participate in the trial any longer, and does not want any further visits or assessments, and does not want any further trial related contact. Sponsor will continue to retain and use all research results that have already been collected for the trial evaluation. All biological samples that have already been collected may be retained and analyzed at a later date (or as required by local regulations). If a patient withdraws consent, the investigator should make a reasonable effort (e.g. telephone, e-mail, letter) to understand the primary reason for this decision and record this information. Trial treatment must be discontinued and no further assessments conducted. Further attempts to contact the patient are not allowed unless safety findings require communication or follow up.

